A BEHAVIORAL INTERVENTION WITH FOSTER FAMILIES

NCT Number: In progress of registering

Date of Original Document: January 1, 2022

STUDY PROTOCOL

Purpose and Aims

The purpose of this study is to test the effects of an easily accessible intervention that is unique for including both caregivers and children living in the home. Three aims will be conducted to: (1) establish the feasibility of the technology-based, family-centered intervention; (2) explore in a preliminary manner the effects of the intervention on stress and relational quality outcomes among family member participants; and (3) explore feasibility and preliminary efficacy of the intervention on diurnal salivary cortisol levels within the foster family population.

Design

This study will use a randomized controlled trial design. Randomization will be used to assign participants into the experimental or control group. Blinding of the two groups to participants will not be done. However, the team will blind the statistical analysis to group with the use of a statistician. Families assigned to the control will have the opportunity to participate in the intervention post- data collection and analysis and outside of the research protocol. The intervention was created in partnership and adapted from the Connected Family Series (CFS) by psychologists at the Karyn Purvis Institute of Childhood Development (KPICD). Adaptation is needed as the original intervention was geared toward adoptive families and excluded foster families. This process is currently occurring, but has not been completed. The intervention also needed content specific to fostering children with special needs. Stress and relational quality outcomes among members will be measured using the concepts of family hardiness, preparedness, and relationship development through a self-report questionnaire which include the Family Hardiness Index, the Integrating Foster Children subscale from the Casey Foster Applicant Inventory, and the Sibling Inventory of Behavior respectively.

Study Timeline

The study will span 6 months to 1 year; 1 month for recruitment and collection of baseline data, 2 months for the intervention, 3 months for post intervention data collection and 3 months for data analysis in 2022. Data will be gathered during the spring and summer of 2022 with the weight-listed control group able to participate in the intervention after data collection of the initial trial period. Dissemination of results is expected by 2023.

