Sample

The study proposed here will follow rigorous guidelines to recruit and screen participants, in order to aid in the study's reproducibility and appropriate application (Friedman et al., 2015). The defined study population is foster families with both permanent and foster children in the home. Inclusion criteria for the study includes the following: 1) licensed foster families, 2) must have at least 1 permanent child (biological or adopted) living in the home before the foster or newly adopted child entered the home, 3) at least one foster or foster-to-adopt child placed in the home, 4) all participants other than the foster or foster-to-adopt child must have English as their primary language or be proficient in English. Families will be recruited through professional organizations such as the Karyn Purvis Institute of Childhood Development (KPICD), the Utah Foster Care Foundation – an organization responsible for the prelicensure training and continuing education of foster parents in the state of Utah, as well as a foster parent support group social media platforms (letter of support on file with [name]). Eligibility criteria ensures that sibling interactions and how they affect placement stability will be captured.

Sample Size Justification

The total sample size for the study (N=130) of families was estimated for 80% power for t-test and ANOVAS, $\alpha < .05$ using G*Power software. Although the exact effect size of the intervention is unknown, we used results from the randomized control trial by Schoemaker et al.

(2020) in which a video intervention to improve parenting among foster families was used and their effect size of 0.34 for differences of the intervention on parenting sensitivity measures using the adapted Ainsworth scales for sensitivity and non-interference. Consistent with Shoemaker et al., a similar sample size was found to be sufficient to detect significant results for the original Connected Family Series. Collection of salivary cortisol to achieve exploratory aim 3 will be done with a smaller sample size of 40, consistent with previous similar feasibility studies for hypothalamic–pituitary–adrenal (HPA)-axis function (Pace et al., 2021).

Participant Recruitment

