Participants screened and deemed to fit inclusion and not exclusion criteria will fill out a demographic survey and intent to offer permanency. Families will also be asked their willingness to participate in salivary cortisol collection. Caregivers will complete the three-pronged battery of assessments containing a total of 52 questions with an expected time to complete of 15 to 20 minutes for all questionnaires, which will be formatted into one questionnaire for participants. The three questionnaires include the Family Hardiness Index, the Sibling Inventory of Behavior, and the Modified Casey Applicant Inventory.

Hardiness - Family Hardiness Index (FHI)

Measurements for family hardiness will be done using the Family Hardiness Index (FHI). The FHI instrument is a 20-item Likert-type scale with a 4-point response scale ranging from false to true about the family situation (McCubbin et al., 1987). Higher scores indicate higher family hardiness. Validity and reliability have been established through positive correlations with family function measures, with an Cronbach's alpha coefficient of .82 with test-retest reliability of .86 (McCubbin et al., 1996). Studies have employed the FHI to accurately indicate a hardiness levels within foster families and those raising children with special needs (Hendrix & Ford, 2003; Roberts et al., 2017). See Appendix D: Family Hardiness Index.

Relationship Development - Sibling Inventory of Behavior (SIB)

The Sibling Inventory of Behavior (SIB) was developed to assess sibling relationships between a typically developing sibling and a child with a disability using a 28-item questionnaire (Schaefer, 1981) and will be used here to assess relationship development. The measure assesses four aspects of sibling relationships: kindness (nine items), avoidance (six items), involvement (seven items), and empathy (six items). Validity of the SIB scales was demonstrated using correlational and observational data with Cronbach alphas ranging from .64 to .81 for each item, indicating that these items are closely related and thus internally consistent (Volling & Blandon, 2003). See Appendix E: Sibling Inventory of Behavior.

Family Preparedness - Modified Casey Foster Applicant Inventory

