Collection of saliva will include two family members: the primary caregiver and the permanent sibling that is closest in age to the foster child. If two permanent children are the same age difference away from the foster child, the permanent sibling with who the foster child interacts with most will be selected. Consent and assent forms will be signed by parent and child. Saliva will be gathered for three consecutive days before the intervention (days 1, 2, and 3) and after the intervention (days 31, 32, and 33); each sampling day, participants will provide a waking, 30 min after waking, and bedtime sample. A two-week window for saliva collection will be allowed depending on when the participating family completes the intervention. Participants passively drool through a straw into a 2mL polypropylene tube and labeled each tube with the time and date. Participants will be instructed not to eat, drink, or brush their teeth 30 minutes before each sample, and to keep completed samples in the refrigerator throughout the study period. Participants will ship saliva samples to the lab and samples will be then stored at -20°C. Saliva samples will be batch assayed in duplicate according to manufacturer instructions for cortisol concentrations using an enzyme immunoassay (EIA) kit (Salimetrics, State College, PA). Inter- and intra-assay coefficients of variability in previous studies by the Pace research team

were 8.16% and 7.74%, respectively. In line with prior work (Zeiders et al., 2014), the following cortisol parameters will be assessed: waking level (Sample 1), bedtime level (Sample 3), the CAR (the difference between Sample 2 – Sample 1), the diurnal slope (the difference between Sample 3 - Sample 1), and the area under the curve (AUC) to assess total cortisol output across the day. AUC will be calculated using the trapezoidal method.

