A BEHAVIORAL INTERVENTION WITH FOSTER FAMILIES

NCT Number: In progress of registering

Date of Original Document: October 25, 2021

STATISTICAL ANALYSIS PLAN

Plan for Data Management/Analysis

Randomization: The central hypothesis will be tested using a randomized controlled trial (RCT) design. The intent of the RCT design is to measure the effectiveness of the intervention and decrease bias through randomization (Montori & Guyatt, 2001). Because severity of disability may affect stress levels in the home, partial stratified randomization for disability severity will be employed. Stratified randomization creates balance between the control and intervention groups. Furthermore, stratification between each group allows for disaggregation of data (Friedman et al., 2015). If the highest-needs children are overrepresented in either the control or intervention groups, inferences could be incorrectly skewed. Families will complete an adapted Autism Behavior Checklist (ABC) before randomization, designed to screen for developmental and behavioral problems in children. The ABC was developed to provide a valid behavior checklist to measure level of behavioral concerns in children with disabilities (Krug, 1980) and has demonstrated intra-rater reliability of $r = 0.87$. Families will be stratified to ensure equal disability severity among groups. The two study groups will include 1) the control group with no intervention and 2) families receiving the intervention. Families will fill out the prescreening tool, be randomly assigned to a group, and receive the survey tools. The same surveys will be collected after the intervention for comparison among groups. Families not assigned to the intervention will be offered the option to receive the intervention after the initial study has concluded. Families participating in the salivary cortisol collection will be randomly chosen from the intervention group.

Statistical analysis will be blinded through use of an independent statistician. STATA statistical software will be used to calculate descriptive statistics, t-tests, correlations, and

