regressions to examine prediction and address the study aims. Consistent with the aims of the study, the primary outcome is to determine the feasibility and effect of the intervention on family hardiness and relationship development, with a secondary outcome of stress levels measured via cortisol levels. We hypothesize that the intervention will improve family hardiness measures and sibling relationships, and that salivary cortisol collection of families participating in the collection of saliva will be feasible within this population. The primary investigator examine potential mediation analysis and multi-level modeling to identify relationships of the concepts and individual characteristics nested within families.

References

Friedman, L. M., Furberg, C. D., DeMets, D. L., Reboussin, D. M., & Granger, C. B. (2015).

Fundamentals of clinical trials (5th ed. 2015 ed.). Cham: Springer International Publishing. <https://doi.org/10.1007/978-3-319-18539-2>

Krug, D. A. (1980). Behavior checklist for identifying severely handicapped individuals with high levels of autistic behavior. *Journal of child psychology and psychiatry*, 21(3), 221-229. <https://doi.org/10.1111/j.1469-7610.1980.tb01797.x>

Montori, V. M., & Guyatt, G. H. (2001). Intention-to-treat principle. *Canadian Medical Association Journal (CMAJ)*, 165(10), 1339-1341.

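### Saliva is collected only from intervention families, so the preliminary-efficacy part of Aim 3 has no control comparison for cortisol

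*SAP*

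**What the plan says.** The third aim under Purpose and Aims in the protocol is to "explore feasibility and preliminary efficacy of the intervention on diurnal salivary cortisol levels within the foster family population". In the SAP's Plan for Data Management/Analysis, the outcome statement ends "with a secondary outcome of stress levels measured via cortisol levels". The only cortisol hypothesis there is that "salivary cortisol collection of families participating in the collection of saliva will be feasible within this population".

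On who is sampled, the Randomization paragraph of the SAP states: "Families participating in the salivary cortisol collection will be randomly chosen from the intervention group". The protocol names no arm for saliva. Its Pre-Intervention Assessment section says "Families will also be asked their willingness to participate in salivary cortisol collection", and its Salivary Cortisol section ties the timing of the second collection to when a family finishes the intervention.

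On numbers, Sample Size Justification says "Collection of salivary cortisol to achieve exploratory aim 3 will be done with a smaller sample size of 40". It does not say whether these are families or individuals, although "Collection of saliva will include two family members". The figure rests on earlier feasibility studies, with no effect size, SD or power given.

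**The concern.** An efficacy statement, even a preliminary one, is a statement about what would have happened without the intervention. The randomised control group supplies that for the surveys. For cortisol the control sample size is zero. Choosing saliva families at random within the intervention group makes them representative of that group but gives no counterfactual.

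Cortisol depends on daily routine, and the protocol's Study Timeline places data collection in spring and summer 2022, so routine may change between the two samplings for reasons unrelated to the intervention. A background shift could then be reported as preliminary efficacy, although the trial already enrols the group that would reveal it.

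There is also a conditional point about blinding. The SAP promises a blinded analysis by an independent statistician. If cortisol data reach that person linked to survey data or arm codes, having a cortisol record identifies the intervention arm. The documents state no safeguard.

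**Working it through.** **The texts side by side.** The aim requires an intervention effect on cortisol. The sampling rule gives 40 from the intervention arm and 0 from control, so no between-arm effect can be estimated. The only comparison across groups that the SAP's Randomization paragraph describes is of the surveys. This conclusion needs no arithmetic. The plan's figure of 40 has no stated inputs, so it cannot be reproduced. The calculations below show only the size of the problem and of the remedy.

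**Inputs**
- From the documents: 40 sampled; two people per family; 130 families with a 50% chance of either arm (65 per arm); alpha .05, taken as two-sided.
- Assumed, because the documents give no values: drift of 0.2 or 0.3 SD of cortisol with no intervention effect; pre-post correlation r of 0.3, 0.5 or 0.7.
- Also assumed: the 0.34 in Sample Size Justification is a standardised mean difference and is carried over to cortisol.
- Caregivers are taken alone: n = 40 if 40 means families, n = 20 if it means individuals.

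**1. How often drift alone gives p<.05 in a one-arm paired test.** The SD of the change is √(2(1−r)). The noncentrality is drift × √n / √(2(1−r)), with n−1 degrees of freedom. For n = 40, drift 0.2 and r = 0.5, the SD of change is 1.000, the noncentrality is 0.2 × √40 = 1.265 and the critical t is 2.023, which gives 0.235.

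| n | Drift (SD) | r = 0.3 | r = 0.5 | r = 0.7 |
|---|---|---|---|---|
| 40 | 0.2 | 0.181 | 0.235 | 0.357 |
| 40 | 0.3 | 0.346 | 0.457 | 0.666 |
| 20 | 0.2 | 0.111 | 0.136 | 0.195 |
| 20 | 0.3 | 0.190 | 0.247 | 0.376 |

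With no drift the rate is 0.050.

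**2. What a between-arm comparison of the same total would give.** For ANCOVA on post-intervention cortisol adjusted for baseline, with n per arm, the 95% half-width is t(.975, 2n−3) × √(2(1−r²)/n). At 20 v 20 and r = 0.5 this is 2.026 × √(2 × 0.75/20) = 2.026 × 0.274 = 0.555 SD.

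| Arms | Quantity | r = 0.3 | r = 0.5 | r = 0.7 |
|---|---|---|---|---|
| 20 v 20 | Half-width (SD) | 0.611 | 0.555 | 0.458 |
| 20 v 20 | Power at 0.34 SD | 0.195 | 0.227 | 0.311 |
| 10 v 10 | Half-width (SD) | 0.900 | 0.817 | 0.674 |
| 10 v 10 | Power at 0.34 SD | 0.117 | 0.132 | 0.171 |

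**3. Whether choosing before allocation needs its own stratum.** Under a 65/65 allocation, the number of 40 pre-chosen families falling in one arm is hypergeometric, with a central 95% range of 15 to 25. At 15 v 25 and r = 0.5 the half-width is 2.026 × √(0.75 × (1/15 + 1/25)) = 0.57, against 0.55 at 20 v 20. For 20 pre-chosen families the range is 6 to 14. At 6 v 14 the half-width is 2.110 × √(0.75 × (1/6 + 1/14)) = 0.89, against 0.82 at 10 v 10.

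**4. What the intervention arm loses.** At r = 0.5 the SD of change is 1, so the half-width of the arm's own pre-post change is t(.975, n−1)/√n: 0.320 SD at n = 40 and 0.468 SD at n = 20.

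**The case against.** The strongest reply is that the plan promises little on cortisol. The aim is worded as exploratory and preliminary, the 40 is justified by feasibility studies, the only cortisol hypothesis is feasibility, and no cortisol efficacy test is specified. The protocol (January 2022) is dated after the SAP (October 2021) and names no arm for saliva. On this view the fault is loose wording. A control comparison with 12–31% power would ask control-arm children for repeated samples in return for a very wide interval.

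Much of this stands as a limit on the point. Feasibility is untouched. The between-arm comparison can only be an estimate. Removing the efficacy wording is a legitimate answer. The drift figures are generic: they do not model the five cortisol parameters in two family roles, and the protocol says the analysis will follow a cited study that is not available here. The blinding point depends on a data flow that the documents do not describe.

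The objection does not remove the mismatch. The protocol's silence on arm does not provide control saliva, and its link between the second collection and finishing the intervention fits intervention-only sampling. Efficacy appears in the aim, and the SAP makes cortisol-measured stress a secondary outcome. No method of analysis borrowed from another study can supply control samples that were never taken. Nor does drawing only from willing families upset the expected split, because any set fixed before a 65/65 allocation divides in the same way.

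**Conclusion.** The concern holds. As written, the plan cannot deliver the efficacy part of Aim 3 or interpret the secondary cortisol outcome as an intervention effect. That conclusion comes from the text and rests on no assumption.

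The size is illustrative. Drift of 0.2 to 0.3 SD alone would give a nominally significant change in 18–67% of trials with 40 caregivers, or 11–38% with 20, for correlations of 0.3 to 0.7. The point should be fixed, but it does not threaten the survey outcomes or cortisol feasibility.

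**What to change.** **Preferred.** Choose the same total of 40 at random, before allocation, from families willing to give saliva. Willingness is already asked, and it can be asked with the prescreening tool, since the SAP's order is "Families will fill out the prescreening tool, be randomly assigned to a group, and receive the survey tools". No extra stratum is needed. Sample both arms on matched dates. Compare post-intervention cortisol between arms, adjusted for baseline, separately for caregivers and siblings, as an estimate with a 95% CI and not as a test. Report feasibility on everyone sampled.

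**Cost.** The number of kits and assays is unchanged. The change needs protocol and SAP text, control-arm consent and assent for saliva, and matched sampling dates for control families. Half as many intervention families are sampled, so the half-width of their own pre-post change rises from 0.32 to 0.47 SD (40 to 20 caregivers, r = 0.5), and the between-arm interval is wide.

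**If intervention-only sampling is kept.** Remove cortisol efficacy from Aim 3 and from the secondary outcome, describe the results as feasibility and descriptive pre-post data, and withhold cortisol data from the statistician until the survey analysis is locked. Dropping the efficacy wording costs only text.

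**Clarify at the same time.** State whether 40 means families or individuals and whether the T3 collection includes saliva. Reconcile the post-intervention sampling on days 31–33 with the two-month intervention period in the Study Timeline. These are separate clarifications and the conclusion does not depend on them.

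### The plan does not commit the T1 score or the severity stratum to the group comparison, so precision that is available at almost no cost may go unused

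*SAP*

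**What the plan says.** The SAP (Plan for Data Management/Analysis) names its methods in one sentence: "STATA statistical software will be used to calculate descriptive statistics, t-tests, correlations, and" "regressions to examine prediction and address the study aims". It gives no model for any regression. It adds that the investigator will look at "potential mediation analysis and multi-level modeling to identify relationships of the concepts and individual characteristics nested within families"; this concerns relationships among concepts, not the difference between arms. The Protocol (Sample Size Justification) says the sample size "was estimated for 80% power for t-test and ANOVAS", which is the only mention of ANOVA, and no ANOVA design is given.

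On the comparison itself, the SAP says: "The same surveys will be collected after the intervention for comparison among groups". The Protocol (Sources of Materials) schedules the surveys before the intervention (T1), after it (T2) and one month later (T3).

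On severity, the SAP says that "partial stratified randomization for disability severity will be employed", because severity may influence stress at home, and that "Families will complete an adapted Autism Behavior Checklist (ABC) before randomization". It gives neither the number of strata nor their cut-points.

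On order of events, the SAP says: "Families will fill out the prescreening tool, be randomly assigned to a group, and receive the survey tools". The Protocol (Design) says participants are not blinded.

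**The concern.** The trial measures each outcome at baseline and stratifies on a factor it expects to be prognostic. Both can narrow the confidence interval for the group difference, but only if the analysis uses them. As written, the statistician could run a T2-only t-test, a change-score t-test or an adjusted regression and comply with the plan each time. The three can differ considerably in precision.

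Aim 2 is described as preliminary, but that does not remove the issue. The SAP includes the effect on family hardiness and relationship development in its primary outcome, and the interval around that effect is what a later trial would be planned on. The blinded independent statistician limits choosing a model by its result, but does not fix the model.

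**Working it through.** **Inputs from the documents.** 130 families (Sample Size Justification); a 50% chance of the intervention (Potential Benefits), so 65 per arm; alpha .05; effect size 0.34. The Family Hardiness Index test-retest reliability is .86, which serves only as an upper anchor for that scale.

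**Assumptions.** Two-sided test; 0.34 read as a standardized mean difference d; one record per family; no dropout; T2 SD = 1. The within-arm T1–T2 correlation r is not given; .3, .5, .7 and .8 are tried. The share of outcome variance explained by the stratum (R²) is not given; 2% to 10% is tried.

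**The plan's own figure.** With d = 0.34, an independent two-sided t-test needs 274 families for 80% power. At 130 the power is 48.6%. The stated 130 therefore does not reproduce under this reading. That is a separate sample-size problem; 48.6% is used below only as the reference.

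**Adjustment for T1, equal SDs at T1 and T2.** Variances relative to the T2-only t-test:
- change score: 2(1 − r)
- T1-adjusted (ANCOVA): 1 − r²
- ANCOVA relative to change score: (1 − r²) / [2(1 − r)] = (1 + r)/2

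| r | Change vs T2-only | ANCOVA vs T2-only | ANCOVA vs change | Saving over the better t-test |
|---|---|---|---|---|
| .3 | 1.40 | 0.91 | 0.65 | 9% |
| .5 | 1.00 | 0.75 | 0.75 | 25% |
| .7 | 0.60 | 0.51 | 0.85 | 15% |
| .8 | 0.40 | 0.36 | 0.90 | 10% |

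Below r = .5 the T2-only test is the better of the two; above it, the change score is.

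**95% CI half-width.** T2-only: 1.979 × √(2/65) = 0.347 SD. Multiplying by the square root of each relative variance gives:
- ANCOVA: 0.331, 0.301, 0.248, 0.208 SD
- change score: 0.411, 0.347, 0.269, 0.220 SD

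**Unequal SDs.** With k = SD(T2)/SD(T1), ANCOVA relative to change score is k²(1 − r²)/(1 + k² − 2rk). The ratio to T2-only stays at 1 − r².
- k = 1.25: 0.78, 0.89, 0.98, 1.00. The saving over the better t-test is 9%, 11%, 2%, 0%.
- k = 0.8: 0.50, 0.57, 0.63, 0.64. The saving is 9%, 25%, 37%, 36%.

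**Stratum alone.** Relative variance is 1 − R², so 0.98 to 0.90. Power at d = 0.34 goes from 48.6% to 49.3% (R² = .02), 50.5% (.05) or 52.7% (.10). If severity is fully balanced between arms, the true size of an unadjusted T2 t-test is 2[1 − Φ(1.96/√(1 − R²))] = 4.8%, 4.4% or 3.9%. Stratification is only partial, so the size should lie between these values and 5%.

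**The case against.** The strongest reply is that the plan does not rule adjustment out. Regressions are listed for addressing the study aims, and one of those aims is the intervention's effect. A regression of T2 on group, T1 and stratum fits that wording, and the ANOVAs could be repeated-measures. This stands: the defect is lack of commitment, and any loss of precision is conditional. A reader might infer that the plan discards its baseline data; the documents do not support that.

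A reader might also take the T2-only column as the loss. At r = .7 or .8 it would make 130 adjusted families worth 130/0.51 = 255 or 130/0.36 = 361 unadjusted ones. But nothing says the T2-only test would be used. Against the change score, which fits the text equally well, the saving at those correlations is 15% or 10% with equal SDs.

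The benefit also depends on when T1 is completed. The SAP lists the surveys after assignment, families are not blinded, and neither document says when they learn their group. T1 answers given after disclosure could be affected by it, which would compromise adjustment and change scores alike. This stands, and the fix is made conditional on it.

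Finally, the documents do not restrict the surveys to one respondent per family. The working assumes one; several would require an allowance for clustering.

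**Conclusion.** The concern holds as a gap in specification with an inexpensive remedy. The comparison model is open, and the options it leaves differ in precision. Given T1 completed before disclosure, adjustment saves about 9% to 25% of the variance over the better simple t-test with equal SDs, over the range of r tried. With an SD ratio between 0.8 and 1.25 the range is 0% to 37%. If the less suitable t-test were chosen, the loss would be larger. All of these rest on an assumed r.

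Nearly all the gain comes from T1. Omitting the stratum costs little and makes the t-test at most mildly conservative.

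Two stronger conclusions might be inferred and are not supported. The first is that an unadjusted comparison would be invalid: randomization protects the T2-only test, and the change-score test too if T1 precedes disclosure. The second is that adjustment repairs the sample size: at 130 families and d = 0.34, 80% power would need r of about .73, which the documents give no basis for assuming. This is a change that should be made, not one on which the trial's validity turns.

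**What to change.** In the SAP (Plan for Data Management/Analysis), state that the main comparison for family hardiness, and for one Sibling Inventory of Behavior score named in advance, is a linear model of the T2 score. Its terms are assigned group, the T1 score of that outcome, and the severity stratum as used in randomization, with its categories defined. Report the adjusted group difference with its 95% CI. Analyse T3 and preparedness in the same way as secondary. If more than one person per family answers, account for clustering by family. A joint mixed model of T2 and T3 is optional.

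State also that T1 is completed before a family is told its allocation. If that cannot be arranged, adjust the main analysis for the stratum only, since the checklist behind it precedes randomization, and show the T1-adjusted result as a sensitivity analysis. This fallback gives up most of the gain: relative variance 0.90 to 0.98 instead of 0.36 to 0.91, both against the T2-only test.

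The cost is SAP wording, including the stratum definition, a few degrees of freedom and one scheduling sentence. No new data are needed.
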